9.2.3. Inclusion Criteria

Patients must meet all of the following inclusion criteria to be eligible for inclusion in the study:

- 1. SARS-CoV-2 diagnosis (as defined in SAP) (index date).
- 2. At least 6 months of continuous enrollment prior to index date.
- 3. Age 18 or older at index date.

For indicated subcohort:

1. Evidence of RA, PsA, or UC diagnosis (Section 9.3) within baseline period (to be defined in SAP) prior to index date.

For non-indicated subcohort:

1. No evidence of RA, PsA, or UC diagnosis (Section 9.3) within baseline period (to be defined in SAP) prior to index date

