Post-SARS Non-TNFi	Baseline Characteristic/Exposure	Evidence of therapy prescribed within 6 months on or after index date.
Post-SARS bDMARD	Baseline Characteristic/Exposure	Evidence of TNFi or non-TNFi on or after index date.
Post-SARS tofacitinib	Baseline characteristic/Exposure	Evidence of therapy prescribed within 6 months on or after index date.
Post-SARS JAK inhibitor	Baseline Characteristic/Exposure	Evidence of therapy prescribed within 6 months on or after index date.
Post-SARS Monotherapy	Baseline characteristic/Exposure	No evidence of MTX or other csDMARD concomitant with post-index advanced systemic therapy (ie, TNFi, non-TNFi, tofacitinib, JAK inhibitor).
Post-SARS Combination therapy	Baseline characteristic/Exposure	Evidence of MTX or other csDMARD concomitant with post-index advanced systemic therapy (ie, bDMARD, tDMARD) and MTX or other csDMARD.
Region	Baseline/potential confounder	Distribution of geographic region at index date.
Insurance	Baseline/potential confounder	Insurance type at index date.
Age	Baseline/potential confounder/risk factor	Continuous age at index date.
Gender	Baseline/potential confounder/risk factor	Woman; Male; Unknown.

Variable	Role	Operational definition ^a
Race	Baseline/potential confounder/risk factor	Race recorded.
Hypertension	Baseline/potential confounder	Diagnosis of hypertension within 6 month baseline period.
Hyperlipidemia	Baseline/potential confounder	Diagnosis of hyperlipidemia within 6 month baseline period.
History of coronary artery disease	Baseline/potential confounder	Diagnosis of coronary heart disease within 6 month baseline period.
History of serious infections	Baseline/potential confounder	Hospitalized infections or use of parenteral antibiotics within 6 month baseline period.
History of hospitalization	Baseline/potential confounder	Days hospitalized within 6 month baseline period.
ILD	Comorbidity/Risk factor	Diagnosis of ILD within 6 month baseline period.
Asthma	Comorbidity/Risk factor	Diagnosis or asthma within 6 month baseline period.
VTE	Comorbidity/Risk factor	Diagnosis of PE or DVT within 6 month baseline period.
Cancer	Risk factor	Diagnosis of cancer within 6 month baseline period.
Other immune deficiencies	Risk factor	Diagnosis of immunodeficiency within 6 month baseline period.
HIV/AIDS	Risk factor	Diagnosis of HIV/AIDS within 6 month baseline period.
Diabetes	Risk factor	Diagnosis of diabetes within 6 month baseline period.

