CKD/Dialysis	Risk factor	Diagnosis of CKD or dialysis procedure within 6 month baseline period.
Liver Disease	Risk factor	Diagnosis of liver disease within 6 month during baseline period.
Corticosteroid Use	Risk factor	Evidence of use within 6 month baseline period.
SARS diagnosis site	Endpoint	Facility location where SARS-CoV-2 was diagnosed (eg, ER, ICU, outpatient).
Hospitalization	Primary Endpoint	Yes/No: hospitalization within 30 days post-SARS-CoV-2 diagnosis.

Variable	Role	Operational definition ^a
ICU admission	Primary Endpoint	Yes/No admission to ICU within 30 days post-SARS-CoV-2 diagnosis.
In hospital death	Endpoint	Discharge diagnosis = death post hospitalization associated with SARS-CoV-2 diagnosis.
All-cause mortality	Endpoint	Death within 90 days post-SARS-CoV-2 infection.
Length of hospital stay	Endpoint	Duration of inpatient stay for visit associated with SARS-CoV-2 diagnosis.
Length of ICU stay	Endpoint	Duration of ICU stay for visit associated with SARS-CoV-2 diagnosis.
Respiratory failure	Endpoint	Diagnosis in conjunction with SARS-CoV-2 diagnosis.
Kidney failure	Endpoint	Diagnosis in conjunction with SARS-CoV-2 diagnosis.
Thrombosis/coagulation events/stroke	Endpoint	Diagnosis in conjunction with SARS-CoV-2 diagnosis.
ARDS	Endpoint	Diagnosis in conjunction with SARS-CoV-2 diagnosis.
Heart failure	Endpoint	Diagnosis in conjunction with SARS-CoV-2 diagnosis.
Sepsis/septic shock	Endpoint	Diagnosis in conjunction with SARS-CoV-2 diagnosis.
Invasive ventilation	Endpoint	Procedure performed during hospitalization associated with SARS-CoV-2 diagnosis.
Non-invasive ventilation	Endpoint	Procedure performed during hospitalization associated with SARS-CoV-2 diagnosis.
ЕСМО	Endpoint	Procedure performed during hospitalization associated with SARS-CoV-2.
Oxygen therapy	Endpoint	Procedure performed during hospitalization associated with SARS-CoV-2 diagnosis.
IV immunoglobulin	Endpoint	Procedure performed during hospitalization associated with SARS-CoV-2 diagnosis.

Variable	Role	Operational definition ^a
Discharge Disposition		Disposition at discharge from hospital stay associated with SARS-CoV-2 diagnosis.

a. Where applicable codes and other definitions to be further defined in Statistical Analysis Plan.

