9.4. Data Sources

The structured data within Optum COVID testing database will be used to identify populations, exposures, confounders and endpoints of interest as described in Section 9.3.

As of 22 April 2020 the Optum COVID database currently includes 32,000 patients who have either been tested for COVID-19 or diagnosed with COVID-19 (regardless of positive/negative result). Refreshes of this data are delivered on a bi-weekly basis through September 2020 and on a monthly cadence from October 2020 – February 2021. This cohort includes details of a patient's office visit and/or hospital stay, including but not limited to: demographic, diagnosis, procedures performed, vital signs and other biometric measures, laboratory results, and prescriptions written and dispensed. All diagnosis data in this study will be obtained from structured data (via ICD-10-CM codes or ICD-9-CM codes where applicable). All drug treatment data will be pulled from prescription written, medication administration, and procedure tables when appropriate (via ICD-9-CM or ICD-10-CM, NDC, CPT, and HCPCS codes).

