9.9. Limitations of the Research Methods

Limitations that are general to claims database analyses and specific to this study should be noted. Diagnosis of autoimmune conditions will be identified using ICD-10-CM diagnosis codes, which are subject to potential miscoding, though presumably without respect to the treatment or outcomes. Where possible, validated algorithms will be used. The baseline period of this study is of limited duration thus baseline comorbidities and risk factors occurring outside of this baseline period may not be captured, which may lead to misclassification.

SARS-CoV-2 is a new disease with evolving diagnostic mechanisms and care. Diagnosis codes have only been established since after the first cases in the US and the validity of the diagnosis codes are unknown. The spectrum of clinical manifestations of SARS-CoV-2 is unknown. Many infected persons are thought to have mild to unrecognizable symptoms and may not present for care or diagnosis. These infections will not be represented in the datasets thus this study is generalizable with respect to more serious sequelae of infection.

Similarly, patients with chronic diseases or in inpatient setting, the elderly, or other risk groups may be more likely to be under ongoing care or thought to be at higher risk and therefore may be more likely to seek care or be referred for testing. Thus differences

between indicated and non-indicated populations may arise from access to care/health behaviors rather than true differences in risk.

The primary analyses are descriptive in nature and inferences regarding association of treatment or indication are not possible. Feasibility of comparative analyses will depend on the number of infected patients with indications/treatments of interest.

Generalizability may be further limited as SARS-CoV-2 testing patterns and treatment are evolving over time.

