- As part of a shared decision-making process between patients and rheumatology providers, select measures to reduce healthcare encounters and potential exposure to SARS-CoV-2 (beyond general preventive measures) may be reasonable, eg, reduced frequency of lab monitoring, optimal use of telehealth, increased dosing intervals between intravenous medications) (M/H).
- If indicated, glucocorticoids should be used at the lowest dose possible to control rheumatic disease, regardless of exposure or infection status (M/H).
- Glucocorticoids should not be abruptly stopped, regardless of exposure or infection status (H).
- If indicated, angiotensin converting enzyme (ACE) inhibitors or angiotensin receptor blockers (ARBs) should be continued in full doses or initiated (M/H).

ONGOING TREATMENT OF STABLE PATIENTS IN THE ABSENCE OF **INFECTION OR SARS-COV-2 EXPOSURE:**

- Hydroxychloroquine or chloroquine (HCQ/CQ), sulfasalazine (SSZ), methotrexate (MTX), leflunomide (LEF), immunosuppressants (eg, tacrolimus, cyclosporine, mycophenolate mofetil, azathioprine), biologics, Janus kinase (JAK) inhibitors and non-steroidal anti-inflammatory drugs (NSAIDs) may be continued (this includes patients with giant cell arteritis with an indication, in whom IL-6 inhibitors should be continued, if available) (M/H).
- Denosumab may still be given, extending dosing intervals to no longer than every 8 months, if necessary to minimize healthcare encounters (M).
- For patients with a history of vital organ-threatening rheumatic disease, immunosuppressants should not be dose-reduced (M).

IN PATIENTS WITH SLE:

• In newly diagnosed disease, HCQ/CQ should be started at full dose, when available (H).

- In pregnant women with SLE, HCQ/CQ should be continued at the same dose, when available (H).
- If indicated, belimumab may be initiated (M).

TREATMENT OF NEWLY DIAGNOSED OR ACTIVE RHEUMATIC DISEASES, IN THE ABSENCE OF INFECTION OR SARS-COV-2 EXPOSURE:

Active Inflammatory Arthritis:

- For patients well-controlled on HCQ/CQ, this disease-modifying anti-rheumatic drug (DMARD) should be continued, when available; when unable to access (including in patients with active or newly diagnosed disease), switching to a different conventional synthetic DMARD (either as monotherapy or as part of combination therapy) should be considered (M/H).

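### Chronic and lifelong conditions are taken only from codes in the 6 months before index, so known disease may be recorded as absent; Section 9.9 admits this and offers no remedy

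*Protocol*

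**What the plan says.** The variables table in Protocol Section 9.3 applies one look-back to almost all comorbidities and risk factors. The variable for history of coronary artery disease is "Diagnosis of coronary heart disease within 6 month baseline period". The entry for HIV is "Diagnosis of HIV/AIDS within 6 month baseline period", for diabetes "Diagnosis of diabetes within 6 month baseline period" and for kidney disease "Diagnosis of CKD or dialysis procedure within 6 month baseline period". Hypertension, hyperlipidemia, ILD, asthma, liver disease, immunodeficiency and cancer have the same window. So do acute or time-limited items: serious infection, days in hospital, corticosteroid use and VTE.

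On the data, Section 9.2.3 requires "At least 6 months of continuous enrollment prior to index date", which sets a floor and not a cap. Section 9.2.1 describes the source as longitudinal health records and does not give the length of history per patient. Section 9.4 states: "All diagnosis data in this study will be obtained from structured data". Section 9.7 rules out imputation.

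Section 9.9 says of the limited window that "baseline comorbidities and risk factors occurring outside of this baseline period may not be captured, which may lead to misclassification". It names no longer look-back and no sensitivity analysis.

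**The concern.** A 6-month window suits events that are recent or not, such as an infection or a steroid course. It suits a lifelong condition less well. Diabetes or HIV last coded 200 days before index is still present at index, but under the Section 9.3 definition it counts as absent. With structured codes as the only source and no imputation, nothing later in the plan would recover it.

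Two things are at stake. First, Section 8 makes the description of comorbidities by subcohort and by baseline treatment stratum a primary objective, so under-counting falls directly on a primary result. Second, Section 9.3 labels these variables as risk factors or potential confounders. If a comparison is added later, as Sections 9.1 and 9.5 allow, adjustment would rest on incompletely captured covariates.

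The loss need not be equal across groups, because a code arises only from contact with care. Section 9.9 itself notes that people with chronic disease may be in more regular care than others. That would give the indicated subcohorts better capture than the non-indicated one, and so an apparent difference in comorbidity where none, or a smaller one, exists.

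**Working it through.** The protocol states no comorbidity prevalence, coding rate or sample size, so there is no figure to reproduce. The three checks below show the mechanism and a range. The first two rest on assumed inputs.

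**1. Share missed, by length of look-back.** Assume that a chronic condition is coded at random at *r* occasions a year. The chance of no code in *T* years is exp(−*rT*).

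| Codes per year (assumed) | 6 months, *T* = 0.5 | 12 months, *T* = 1 | 24 months, *T* = 2 |
|---|---|---|---|
| 1 | exp(−0.5) = 61% | exp(−1) = 37% | exp(−2) = 14% |
| 2 | exp(−1) = 37% | exp(−2) = 14% | exp(−4) = 2% |
| 4 | exp(−2) = 14% | exp(−4) = 2% | exp(−8) = 0.03% |

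**2. Effect on the tables.** Assume a true prevalence *p* of 20% and an outcome risk of 30% with the condition and 10% without. With capture *s*, the observed prevalence is *ps*. The share of the apparently free group that has the condition is *f* = *p*(1−*s*) / [*p*(1−*s*) + 1−*p*]. The outcome risk in that group is 0.30*f* + 0.10(1−*f*).

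| Capture (assumed) | Observed prevalence | Apparently free patients who have it | Risk in apparently free group (true 10%) |
|---|---|---|---|
| 80% | 16% | 0.04/0.84 = 4.8% | 11.0% |
| 60% | 12% | 0.08/0.88 = 9.1% | 11.8% |
| 40% | 8% | 0.12/0.92 = 13.0% | 12.6% |

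Two groups with the same true prevalence of 20%, one captured at 80% and the other at 60%, would show 16% and 12%. That is a gap of 4 percentage points produced by capture alone.

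**3. Overlap of the look-back with the pandemic.** Take a 183-day window and assume that any restriction of care began on 1 March 2020. The share of the window on or after that date is:

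- index 1 February 2020: 0%
- index 15 March 2020: 14/183 = 8%
- index 30 April 2020: 60/183 = 33%
- index 30 June 2020: 121/183 = 66%
- index 1 September 2020 and later: 100%

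The earliest patients are therefore observed over months that are mostly pre-pandemic.

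**The case against.** The strongest defence is that a fixed 6-month window is a reasonable choice. It equals the only history that every patient must have, so all are observed for the same time. Using all available records instead would make capture depend on record length, which may itself differ between groups. This stands, and it is why the 6-month table should stay and the longer look-back should be common rather than unlimited. It does not explain why no second look is taken.

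The limitation is also disclosed in Section 9.9. That is true, but disclosure neither reduces nor measures the misclassification. Footnote a of the Section 9.3 table leaves codes and other definitions to the SAP, which is not shown. The 6-month window for comorbidities is nevertheless written into the protocol, whereas Section 9.2.3 expressly defers the window for RA, PsA and UC.

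The coding rates above are assumptions. Patients in a treatment stratum must have a prescription in the same 6 months, so those with no recorded activity cannot be in one, and the 61% figure is not shown to apply there. A prescription for joint or bowel disease does not guarantee a code for diabetes or coronary disease, however. The primary analyses are descriptive, so the confounding consequence arises only if a comparison is added. Cancer does not belong with lifelong conditions: an unlimited look-back would mix remote with recent disease.

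A reader might infer two stronger points that the documents do not support.

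- **That the protocol says care was restricted during the look-back.** Section 9.2.2 calls access only potentially restricted, and says so of patients identified at the start of the pandemic. Check 3 shows that their windows lie mostly before it. The protocol does not say that care stayed restricted later.
- **That capture is worse for oral than for infused drugs.** No section gives visit frequency by route, and the strata are drug classes. Appendix 1 mentions "select measures to reduce healthcare encounters and potential exposure to SARS-CoV-2", but only as something that may be reasonable in a shared decision. One of its examples is longer gaps between infusions, which points the other way.

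**Conclusion.** The point holds as a design weakness that the protocol admits and leaves without a remedy. As written, Section 9.3 may record patients with known chronic disease as free of it, and this bears on a primary objective. The direction is under-counting. Under-capture may also differ between indicated and non-indicated subcohorts, on the reasoning in Section 9.9 about ongoing care.

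The size cannot be computed from the protocol. On the assumption of random coding 1 to 4 times a year, 61% to 14% of affected patients would be missed in 6 months and 14% to under 0.1% in 24 months. How much a longer look-back recovers in practice depends on how many patients have the history, which the protocol does not state.

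**What to change.** - **Section 9.3, unchanged part.** Keep 6 months for acute history, drug exposure, corticosteroids and recent events such as VTE.
- **Sections 9.3 and 9.7, added part.** For coronary disease, ILD, asthma, diabetes, hypertension, hyperlipidemia, CKD, liver disease, HIV/AIDS and immunodeficiency, add a second ascertainment with a longer common look-back, for example 12 or 24 months, in patients who have that history. Report it by subcohort and treatment stratum beside the 6-month table, with the median available history per stratum.
- **Cancer.** Report separately as recent and as any history.
- **Any later adjusted comparison.** Repeat it with the longer look-back as a sensitivity analysis.

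The cost is a longer query on the same source and one extra table. That table covers only patients with longer records, who may differ from the rest, so it supplements the 6-month table and does not replace it.

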9.3. Variables

Variable	Role	Operational definition ^a
SARS-CoV-2 Diagnosis	Inclusion criteria	SARS-CoV-2 diagnosis.
Rheumatoid Arthritis	Subcohort identification	RA diagnosis in baseline period.
Psoriatic Arthritis	Subcohort identification	PsA diagnosis in baseline period.
Ulcerative Colitis	Subcohort identification	UC diagnosis in baseline period.
Non-indicated subcohort	Inclusion criteria/Subcohort identification	Absence of RA, PsA, and UC codes within baseline period.
SARS-CoV-2 Diagnosis Date	Exposure/Index date	Date associated with SARS-CoV-2 diagnosis.
Baseline systemic therapy	Baseline Characteristic/Exposure	Evidence of therapy prescribed 6 months prior to index date.
		Categorical: csDMARD, TNFi, non- TNFi, tofacitinib, JAK inhibitor (as monotherapy or combination therapy).
Baseline csDMARD	Baseline Characteristic/Exposure (Comedication)	Evidence of therapy prescribed within 6 months prior to index date.
Baseline TNFi	Baseline Characteristic/Exposure	Evidence of therapy prescribed within 6 months prior to index date.
Baseline Non-TNFi	Baseline Characteristic/Exposure	Evidence of therapy prescribed within 6 months prior to index date.
Baseline bDMARD	Baseline Characteristic/Exposure	TNFi or non-TNFi prescribed within 6 months prior to index date.
Baseline tofacitinib	Baseline characteristic/Exposure	Tofacitinib Evidence of therapy prescribed within 6 months prior to index date.
Baseline JAK inhibitor	Baseline Characteristic/Exposure	Evidence of therapy prescribed within 6 months prior to index date.
Baseline Monotherapy	Baseline characteristic/Exposure	No evidence of MTX or other csDMARD concomitant with baseline advanced systemic therapy (ie, TNFi, non-TNFi, tofacitinib, JAK inhibitor).
Baseline Combination therapy	Baseline characteristic/Exposure	Evidence of MTX or other csDMARD concomitant with baseline advanced systemic therapy (ie, tofacitinib, bDMARD, JAK inhibitor, csDMARD) and MTX or other csDMARD.

Variable	Role	Operational definition ^a
Post-SARS systemic therapy	Baseline Characteristic/Exposure	Evidence of therapy prescribed within 6 months after index date.
		Categorical: csDMARD, TNFi, non-TNFi, tofacitinib, JAK inhibitor (as monotherapy or combination therapy).
Post-SARS csDMARD	Baseline Characteristic/Exposure (Comedication)	Evidence of therapy prescribed within 6 months on or after index date.
Post-SARS TNFi	Baseline Characteristic/Exposure	Evidence of therapy prescribed within 6 months on or after index date.

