9.7. Data Analysis

After selection of the study population, summary statistics of baseline variables will be determined for the baseline period. The index date for each patient is defined as the first date that the study inclusion criteria are satisfied. Baseline variables will be summarized as

appropriate for categorical and continuous variables with 95% CI provided to show precision of the estimate.

Among patients who are included in the study, outcomes will be included that occur during the risk window from index date until the first of death (based on discharge status), 3 months post-SARS-CoV-2 diagnosis, or end of study period/datacut.

The endpoints of interest within each indication, non-indicated subcohort and indication/treatment combination will be summarized as appropriate for categorical and continuous variables with 95% CI provided to show precision of the estimate.

The handling of missing data will be described in the SAP. No variables will be imputed.

Detailed methodology for summary and statistical analyses of data collected in this study will be documented in a Statistical Analysis Plan (SAP), which will be dated, filed and maintained by the sponsor. The SAP may modify the plans outlined in the protocol; any major modifications of primary endpoint definitions or their analyses would be reflected in a protocol amendment.

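### Diagnosis site belongs to the index event but serves only as an endpoint, so pooled hospitalization and ICU proportions are not separated by where patients were diagnosed

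*Protocol*

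**What the plan says.** In the variables table of Section 9.3, SARS diagnosis site is defined as "Facility location where SARS-CoV-2 was diagnosed (eg, ER, ICU, outpatient", and its only role is Endpoint. The same table defines the index date as "Date associated with SARS-CoV-2 diagnosis". Region and insurance type, also taken at the index date, carry a baseline/potential confounder role.

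The two primary endpoints count from the same date: "Yes/No: hospitalization within 30 days post-SARS-CoV-2 diagnosis" and "Yes/No admission to ICU within 30 days post-SARS-CoV-2 diagnosis". Section 9.7 states that "outcomes will be included that occur during the risk window from index date" onward. It then lists the groups in which endpoints are summarized: each indication, the patients with none of the three conditions, and each treatment within an indication. Diagnosis site is not in that list, and no other section of the protocol makes it a baseline variable, confounder or stratifier.

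The protocol itself links setting to the chance of being tested. Section 9.2.2 puts hospitalized patients in the first testing priority and expects testing to change over the study. Section 9.9 says that "patients with chronic diseases or in inpatient setting, the elderly, or other risk groups may be more likely to be under ongoing care" and so more likely to be referred for testing.

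**The concern.** A patient found positive while already on a ward or in the ICU has largely settled the hospitalization or ICU question at time zero. For a patient diagnosed as an outpatient, the 30-day proportion measures what happens next. A pooled proportion is a weighted average of the two, and the weight is the share diagnosed in hospital.

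That share depends on who was tested and where, as well as on how ill patients were when they presented. Section 9.1 plans repeated data cuts and asks whether manifestations differ by indication and treatment, so the pooled proportions will be read side by side across groups and calendar time. Diagnosis site is the listed variable that would most directly show how much of a difference comes from setting, but the protocol uses it only as one more result.

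**Working it through.** The protocol states no event rate, sample size or share diagnosed in hospital, so there is no figure to reproduce. The check has a textual part and an illustrative part.

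**Text.**
- Index event: the SARS-CoV-2 diagnosis (Sections 9.2.3 and 9.3). Site describes that event, so it is fixed at time zero.
- Comparable variables: region and insurance are fixed at the same date and have a baseline role. Site does not.
- Endpoint summaries: the groups named in Section 9.7 do not include site.
- Footnote a of Section 9.3 sends codes and other definitions to the SAP. The role column is fixed in the protocol.

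**Illustration 1: equal within-site risks, different mix.** All inputs are assumed. Let h be the share diagnosed in hospital. In every group, 90% of those patients and 6% of the others count as hospitalized.

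Overall proportion = 0.90h + 0.06(1 − h)

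- h = 15%: 0.135 + 0.051 = 18.6%
- h = 20%: 0.180 + 0.048 = 22.8%; ratio to 18.6% = 1.23
- h = 25%: 0.225 + 0.045 = 27.0%; ratio = 1.45
- h = 30%: 0.270 + 0.042 = 31.2%; ratio = 1.68

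The within-site risks are identical throughout. Only the mix changes.

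**Illustration 2: a wider range.** Let s be the share already in hospital at diagnosis, all counted as events, and r the 30-day risk in patients diagnosed as outpatients.

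P = s + (1 − s)r

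With r = 10%:

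| s | P | outpatient-diagnosed group alone |
|---|---|---|
| 5% | 14.5% | 10% |
| 10% | 19% | 10% |
| 20% | 28% | 10% |
| 30% | 37% | 10% |
| 40% | 46% | 10% |

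Over r = 5% to 20% and s = 5% to 40%, P runs from 9.75% (0.05 + 0.95 × 0.05) to 52% (0.40 + 0.60 × 0.20). Patients already in hospital make up s/P of the counted events, from 21% (0.05/0.24, at r = 20%) to 93% (0.40/0.43, at r = 5%).

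**Illustration 3: the opposite counting rule.** The endpoint definitions do not say how a patient already admitted at diagnosis is counted; the SAP may. If such patients stay in the denominator but are not events, the proportion is (1 − s)r. At r = 10% it falls from 9.5% (s = 5%) to 6% (s = 40%). The direction reverses, but the proportion still moves with setting alone.

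These illustrations use two groups and do not place ER diagnoses in either. They show how a mixture behaves. They do not estimate this study's data.

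**The case against.** The strongest reply is that the label does no harm. Section 9.7 summarizes baseline variables and endpoints alike with 95% CIs, so the distribution of site will appear for each group under either role. Relabelling alone changes no number. That stands: the substance is the added breakdown, not the word Endpoint.

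Second, site is a fair marker of severity at presentation, and several other endpoints, such as respiratory failure and ARDS, may also be present at diagnosis. That stands too. A reader might infer that site should leave the outcome tables, or that hospitalization should be read only from patients diagnosed outside hospital. The documents do not support either step. If a condition or therapy worsens early disease, more of those patients will first be diagnosed in hospital; restricting to the others would condition on early severity and discard the cases of most interest.

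Third, a reader might infer that the mix distorts comparisons between treatments. Section 9.2.2 argues that, within an indication, the prescribed regimen is unlikely to determine referral for testing unless it is linked to symptomatic disease. The exception leaves the question open, but nothing in the protocol shows such a difference. The point rests on indications, indicated against non-indicated patients, and calendar time.

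Fourth, Section 9.9 already discloses testing differences and says that inferences about treatment or indication are not possible, and Section 9.7 leaves detailed methodology to the SAP, which was not available here and may add a split by site. Disclosure does not show how large the effect is, however. Section 7 also states the aim as learning whether tofacitinib modifies risk, so side-by-side reading is to be expected.

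**Conclusion.** The point holds as a cheap improvement. The protocol records a variable fixed at the index date, gives it only an endpoint role, and does not use it in the endpoint summaries that Section 9.7 names. The pooled 30-day hospitalization and ICU proportions can therefore differ between groups or data cuts because of the share already in hospital at diagnosis.

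The size cannot be derived from the document. The contrast of 27.0% with 18.6% (ratio 1.45) rests wholly on assumed within-site risks of 90% and 6%, held equal across groups, and assumed shares of 25% and 15%. The ratio runs from 1.23 to 1.68 when the higher share is 20% to 30%. The figures show that the mix can matter; they do not show that the study's results are biased.

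**What to change.** In Section 9.3, give SARS diagnosis site an index characteristic/stratifier role in addition to its present one, and keep its tabulation as a marker of severity at presentation.

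In Section 9.7, add that hospitalization, ICU admission and mortality will be reported by diagnosis setting (outpatient, ER, inpatient/ICU) alongside, not instead of, the overall proportions. Add a sentence saying that site reflects both testing practice and severity at presentation, so neither the overall nor the site-specific figures should be read alone.

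The cost is one added role, one extra set of table columns and no new data. The downside is small cells, and so wide intervals, in the treatment strata.
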